4.5.2. Procedure at the first interim analysis

The first interim analysis is planned for when 60 patients complete the 7 day visit. At this analysis, conditional power (CP) will be calculated for the primary endpoint. If CP < 5%, a non-binding recommendation will be made to stop for futility.

4.5.3. Procedure at the second interim analysis

The second interim analysis is planned for when for when 120 patients complete their 7 day visit.

Efficacy stopping: An early efficacy stopping boundary of Z > 2.5093 (one-sided P < 0.0060) will be used for all efficacy endpoints. This boundary is the group sequential boundary derived from the Lan-DeMets O'Brien Fleming spending function at 2/3 information fraction. Early stopping for efficacy will be recommended only if both the primary endpoint and secondary endpoint cross the same boundary. If the study continues, both endpoints will be tested against the group sequential boundary 1.9929 at the final analysis in a sequential manner -- the secondary endpoint is tested if the primary endpoint reaches statistical significance -- to preserve the study-wise type 1 error rate at one-sided level 0.025.

If the study is not stopped for efficacy, the interim results will be classified into different zones depending on estimation of the conditional power on the primary endpoint and, separately, on the secondary endpoint. Based on the interim zone, one of the following actions will be recommended:

- Stop the study for futility (non-binding stop).
- Continue the study until reaching the planned 180 evaluable patients (approximately 225 enrolled).
- Continue the study and increase the sample size up to a maximum of 270 evaluable patients (approximately 338 enrolled).

Details on the boundaries of these interim zones and specific actions to be taken within these zones are deferred to a restricted Simulation Report whose circulation is limited to a core study team to include the ISC and DMC in order to minimize the possibility of operational bias.

4.5.4. Procedure at the final analysis

At the time of the final analysis, hypothesis testing for the primary and secondary endpoints will be performed using a weighted combination statistic (Lehmacher and Wassmer 1999; Cui et al. 1999), whereby the Z-statistic from the first stage of the study (the first 120 patients, i.e., 2/3 of the planned information), Z_1 , is combined with the independent Z-statistic from the remaining patients, Z_2 , using prespecified weights $w_1 = \sqrt{0.67}$ and $w_2 = \sqrt{0.33}$ to form a combination statistic $Z^* = w_1 Z_1 + w_2 Z_2$. These weights are used regardless of whether the sample size is increased beyond 180. If $Z^* > 2.5093$, statistical significance is achieved for that endpoint.

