4.2. Sample Size Justification

Sample size and power was determined through simulations. The study will follow an adaptive group sequential design with unblinded sample size re-assessment. In order to assure 180 evaluable patients with 7 day (+/- 1day) data and assuming a 20% dropout rate, approximately 225 patients will be enrolled initially. An interim analysis for futility (non-binding stop) will occur after the first 60 patients complete their 7 day visit, and another interim analysis will be performed for efficacy after 120 patients for futility stopping, early efficacy stopping on the primary endpoint and secondary endpoint, and sample size re-assessment (SSR). The total sample size may be increased up to approximately 338 patients after the second interim analysis to ensure up to 270 evaluable patients.

Based on prior feasibility studies (Bath et al., 2016) the primary endpoint is hypothesized to have an odds ratio of 2.23 favoring the PES group. For the secondary endpoint, the difference in mean DSRS between treatment groups is expected to be 1.75. A common standard deviation of 4 is assumed for DSRS in both treatment groups. With these effect sizes, the power is 95% for significance on the primary endpoint and 85% for significance on both endpoints. Additional simulation results under different assumptions are provided in the Simulation Report.

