4.3. General Statistical Methods and Data Handling

4.3.1. General Methods

All output will be incorporated into Microsoft Excel or Word files, sorted and labeled according to the International Conference on Harmonisation (ICH) recommendations, and formatted to the appropriate page size(s).

Tabulations will be produced for appropriate demographic, baseline, efficacy and safety parameters. For categorical variables, summary tabulations of the number and percentage within each category (with a category for missing data) of the parameter will be presented. For continuous variables, the mean, median, standard deviation, minimum and maximum values will be presented. Time to event data will be summarized using Kaplan-Meier Methodology using 25th, 50th (median), and 75th percentiles with associated 2-sided 95% confidence intervals, as well as percent of censored observations.

Formal statistical hypothesis testing will be performed on the primary and secondary efficacy endpoints with all tests conducted at the 1-sided, 0.025 level of significance. Summary statistics will be presented, as well as confidence intervals on selected parameters, as described in the sections below.

For all analyses, baseline will be defined as the most recent measurement prior to the date and time of the administration of active treatment with Pharyngeal Electrical Stimulation or a sham treatment. Therefore, baseline may be on the same day as the start of study treatment, but prior to the administration of the study treatment.

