4.5.5. Type 1 Error Control

To see that Type 1 error is theoretically controlled even though sample size may be modified in a data-dependent manner, note that under the null hypothesis for the primary endpoint, the incremental statistics for the 2 stages, are independent with asymptotic N(0,1) distribution, regardless of final sample size.

Therefore the final test statistic is normal with mean 0 and variance $w_1^2 + w_2^2 = 1$. It follows that the joint distribution of $w_1Z_1 + w_2Z_2$ is the same as for the standard group sequential test with correlation w_1 at interim, as shown by Cui, Hung and Wang (1999). Because the pre-specified fixed weights w_1 and w_2 are used regardless of whether the sample size is modified based on interim data, the combination statistic with standard group sequential efficacy boundaries properly controls type 1 error. The same principles apply to the secondary endpoint.

Results of simulations performed under various null scenarios confirming type 1 error control are summarized in the Simulation Report.

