4.6.2 Secondary Efficacy Analysis

The secondary endpoints are FIOS and DSRS 7 days (+/- 1 day) after completion of investigational treatment.

The ordered categorical endpoint of FIOS will be analyzed by a Cochran-Mantel-Haenszel (CMH) test stratified by site and baseline PAS, using the modified ridit score and test of "row mean scores different" to take into account the ordered nature of the response.

The secondary endpoint of DSRS will be modeled by an ANCOVA model with treatment, center, baseline PAS and baseline DSRS as predictors, and will be tested for statistical significance provided the primary endpoint is found to be statistically significant. The ITT population will be used.

Missing data on the secondary endpoint will not be imputed for the purpose of significance testing.

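### SAP 4.5.4 uses the interim boundary, 2.5093, as the final critical value where SAP 4.5.3 sets 1.9929; following 4.5.4 would cut one-sided alpha from 0.025 to at most 0.0099 and cost power

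*SAP*

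**What the plan says.** SAP 4.5.3 sets the early efficacy boundary at 2.5093 (one-sided p below 0.0060) and attributes it to Lan-DeMets O'Brien-Fleming spending at an information fraction of 2/3. If the study continues, "both endpoints will be tested against the group sequential boundary 1.9929 at the final analysis in a sequential manner", and the stated purpose is "to preserve the study-wise type 1 error rate at one-sided level 0.025".

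SAP 4.5.4 then defines the final combination statistic `Z*`, with weights √0.67 and √0.33, and closes with a different criterion: "If $Z^* > 2.5093$, statistical significance is achieved for that endpoint".

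Three other places bear on which value is meant:

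- SAP 4.3.1 requires "all tests conducted at the 1-sided, 0.025 level of significance".
- SAP 4.5.5 argues that "the combination statistic with standard group sequential efficacy boundaries properly controls type 1 error".
- SAP 4.2 states that "the power is 95% for significance on the primary endpoint and 85% for significance on both endpoints".

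The protocol gives no boundary and refers to the SAP for the decision rules.

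**The concern.** This is the success criterion for the primary endpoint and, through the sequential testing, for the secondary endpoints. A final `Z*` between 1.9929 and 2.5093 (one-sided nominal p from 0.0231 down to 0.0060) wins under 4.5.3 and fails under 4.5.4. If the result fell there, choosing the lower threshold after unblinding would look post hoc in a study meant to support a de novo submission. Choosing the higher one would give up power that the design had already paid for. A programmer would most naturally implement 4.5.4, because it is the section on the final analysis.

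The ambiguity may also reach the interim decisions. SAP 4.5.1 defines conditional power as the chance of significance at the planned final analysis but does not say against which critical value.

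**Working it through.** **Inputs.** From SAP 4.3.1 and 4.5.3: one-sided level 0.025, O'Brien-Fleming-type spending, t = 2/3. From 4.5.4: the weights. From 4.2: power 95% for the primary endpoint, DSRS difference 1.75, SD 4. From protocol 9.2: power of at least 90%. The first interim analysis is for futility only and spends no alpha.

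**1. The SAP's own boundaries.** The alpha spent at t = 2/3 is 2·(1 − Φ(2.2414/√(2/3))) = 0.00605, which gives an interim boundary of 2.5093. Take the two statistics as bivariate normal with correlation √(2/3) and solve for a total of 0.025: the final boundary is 1.9929. Both match 4.5.3 to four decimals.

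**2. One-sided level for each rule.**

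| Interim / final boundary | Correlation √(2/3) | Weights 0.67 / 0.33 |
|---|---|---|
| 2.5093 / 1.9929 | 0.0250 | 0.02498 |
| 2.5093 / 2.5093 | 0.00986 | 0.00984 |
| final test only, 2.5093 | 0.00605 | 0.00605 |

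The rounded weights therefore do not explain the discrepancy.

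**3. Primary endpoint, fixed at 180 evaluable patients with no sample size increase.** The documents do not give the category probabilities or the within-patient correlation, so the drift (the mean of the final statistic) is solved from an assumed power at the correct boundaries.

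| Power at 2.5093 / 1.9929 | Drift | Power with 2.5093 at both looks | Final test only |
|---|---|---|---|
| 95% | 3.625 | 88.0% | 86.8% |
| 90% | 3.261 | 79.3% | 77.4% |

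The share of trials ending between the two values is 7.0% (95% effect) or 10.7% (90% effect) if a trial whose primary statistic crosses at the interim is set aside. Early stopping requires both endpoints to cross, so a trial can continue after a primary-only crossing. Counting every final `Z*` in the gap gives 8.1% and 12.4%.

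**4. Larger final sample.** If every trial went to 270, stage 2 would have 150 patients. With drift 3.625 the mean of `Z*` is 3.625·(2/3 + √(1/3)·√(150/180)) = 4.327, and power at 2.5093 is Φ(4.327 − 2.5093) = 96.5%. The loss in step 3 is thus a loss at a given sample size, not a cap on attainable power.

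**5. DSRS at 180**, assuming 1:1 allocation and taking SD 4 as the residual SD. The standard error is 4·√(2/90) = 0.596 and the drift is 1.75/0.596 = 2.935.

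- Power at the final test: Φ(2.935 − 1.9929) = 83% and Φ(2.935 − 2.5093) = 66% (69% if an interim crossing counts).
- Observed difference needed: 1.9929·0.596 = 1.19 points and 2.5093·0.596 = 1.50 points.

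The analysis is an "ANCOVA model with treatment, center, baseline PAS and baseline DSRS as predictors", so the residual SD may be below 4, but the SAP does not give it. At an assumed 3.5, power at 2.5093 is 80%.

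**6. Conditional power at 60 patients (t = 1/3).** Under the observed trend, conditional power is below 5% when Z < (c − 1.645·√(2/3))·√(1/3). This is 0.38 for c = 1.9929 and 0.67 for c = 2.5093. With drift 3.625 the chance of a mistaken futility signal would be 4.3% or 7.8%. The documents do not say which c applies.

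**The case against.** The strongest reply is that the intent can be recovered. Section 4.5.3 names 1.9929 as the final boundary and gives its purpose, 4.3.1 requires 0.025, and 4.5.5 relies on standard boundaries. One sentence conflicts, and it errs on the safe side. That is right about intent and about the direction of the error. It does not remove the need for correction, because the conflicting sentence is the operative one for the final analysis.

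The power figures can also be challenged, and here part of the objection stands:

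- SAP 4.2 reports simulated power for a design with sample size re-assessment, whereas step 3 fixes the size at 180. With three assumed promising zones (conditional power 0.2–0.8, 0.3–0.9 and 0.1–0.95, each increasing to 270) and the effect recalibrated to 95%, power at 2.5093 is about 89–90% and the disputed share about 5–6%. The loss is somewhat smaller but remains.
- Because both endpoints must cross to stop early, the level for one endpoint under the correct pair lies between 0.0231 and 0.0250, and under 4.5.4 between 0.0060 and 0.0099. All these figures are upper limits or ranges.
- "A common standard deviation of 4 is assumed for DSRS in both treatment groups", yet with that SD as residual SD, DSRS alone reaches only 83% at 180 with the correct boundary, already below the 85% stated for both endpoints. The simple model does not reproduce the SAP's figure, and it ignores the gatekeeping. It shows the direction and rough size of the loss and nothing finer.
- Nothing indicates that conditional power was computed with 2.5093, and the futility rule is non-binding. Step 6 shows why the value should be named; it is not evidence of a further error.

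**Conclusion.** The concern holds: 2.5093 in SAP 4.5.4 is wrong as written. It contradicts 4.5.3 and does not deliver the 0.025 that the SAP requires. The boundary calculation rests only on figures in the SAP and is exact: 0.0250 with 1.9929, against at most 0.0099 with 2.5093.

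Type 1 error is not inflated. The harm is an ambiguous success threshold and lost power: roughly 5 to 7 percentage points for an effect with 95% power, depending on the unseen sample size rule, and about 11 points for a 90% effect at a fixed 180. These power figures are illustrations that take the stated power as given. Whether the stated 95% and 85% were simulated with 1.9929 cannot be checked without the Simulation Report. Because the number decides whether the trial succeeds, it must be corrected.

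**What to change.** In SAP 4.5.4, replace 2.5093 by 1.9929 as the critical value for the final `Z*` of each endpoint. In 4.5.1, add a sentence that conditional power is computed against 1.9929. Confirm that the Simulation Report used 1.9929 for power, conditional power and the interim zones, and restate those figures if it did not. While editing, note that 4.5.1 defines a Z statistic for the primary endpoint and for the ANCOVA of DSRS but not for the CMH test of FOIS, so the threshold has nothing to attach to there until one is defined.

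Make the change before any unblinded look. If one has already taken place, people without access to the interim results should make the correction and date it, giving the conflict with 4.5.3 as the reason.

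The cost is one number, one sentence and a check of the report. No patients are added, and one-sided type 1 error stays at 0.025.

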4.5.5. Type 1 Error Control

To see that Type 1 error is theoretically controlled even though sample size may be modified in a data-dependent manner, note that under the null hypothesis for the primary endpoint, the incremental statistics for the 2 stages, are independent with asymptotic N(0,1) distribution, regardless of final sample size.

Therefore the final test statistic is normal with mean 0 and variance $w_1^2 + w_2^2 = 1$. It follows that the joint distribution of $w_1Z_1 + w_2Z_2$ is the same as for the standard group sequential test with correlation w_1 at interim, as shown by Cui, Hung and Wang (1999). Because the pre-specified fixed weights w_1 and w_2 are used regardless of whether the sample size is modified based on interim data, the combination statistic with standard group sequential efficacy boundaries properly controls type 1 error. The same principles apply to the secondary endpoint.

Results of simulations performed under various null scenarios confirming type 1 error control are summarized in the Simulation Report.

4.6. Subject Disposition

A tabulation of subject disposition will be tabulated, including the number screened, the number received active treatment of PES, the number received a sham treatment, the number in each subject population for analysis, the number that withdrew prior to completing the study, and reasons for withdrawal.

A by-subject listing of study completion information, including the reason for premature study withdrawal, if applicable, will be presented.

4.7. Demographic and Baseline Characteristics

Baseline, demographic and medical history information will be summarized for the Roll-in, Safety, ITT, and PP populations using descriptive statistics. Summaries will be provided by treatment group, stratification factors, and other key baseline parameters when applicable. No formal statistical testing will be performed.

Demographic, Baseline and medical history data will be provided in data listings.

4.8. Efficacy Evaluation

4.6.1 Primary Efficacy Analysis

The primary endpoint is trichotomized PAS on each bolus, determined by VFSS 48 hours (+/- 24 hours) after completion of PES treatment. The three ordinal PAS categories are defined as Safe (PAS 1-3), Penetration (PAS 4-5), and Aspiration (PAS 6-8). Each patient contributes 12 measurements to the primary endpoint, of which six are from boli of a thin consistency and 6 are from boli of a nectar consistency.

The ITT population will be used for the primary analysis.

A cumulative logistic model will be used to analyze the primary endpoint, and a sandwich variance estimator via a generalized estimating equations approach will be used to account for correlated PAS outcomes within each patient.

The statistical model for the primary analysis will include treatment, bolus consistency, baseline maximum PAS, and treatment by consistency interaction as predictors. The response of individual i on bolus t is coded as $y_{it} = 1$ for a safe swallow, $y_{it} = 2$ for a swallow resulting in penetration, and $y_{it} = 3$ for a swallow resulting in aspiration. The log odds of a swallow with response $\leq j$ conditional on predictors x_{it} is modeled as

$$logit(P(y_{it} \le j | x_{it}))$$

$$= \beta_j + \beta_{base} * base_{it} + \beta_{trt} * trt_i + \beta_{nectar} * nectar_t + \beta_{trt*nectar} trt_i * nectar_t$$

with ordered intercept terms $\beta_1 < \beta_2$, a treatment indicator trt_i (1=PES, 0=control), and a consistency indicator $nectar_i$ (1=nectar, 0=thin). The maximum PAS (1-8) of individual i across all pre-treatment swallows of a given consistency at baseline is denoted $base_{it}$. The GEE approach with robust sandwich estimator is used to account for within subject correlation.

Missing PAS data will be imputed in the primary analysis. PAS values that are missing due to application of VFSS stopping criteria will be assigned the worst (highest) post-treatment PAS value. For patients who have no post-treatment PAS data due to lost-to-follow-up or death, the post-treatment PAS values will be imputed from baseline PAS values and other patient baseline characteristics using multiple imputation. In addition, tipping point analysis will be performed as a sensitivity analysis.

The estimated treatment effect in the logistic model will be presented along with standard error. The treatment effect will also be presented as an odds ratio with 95% confidence interval.

Sensitivity analysis will be performed in which missing values are ignored. Analyses of the primary endpoint with and without imputation will also be performed on the per protocol population.

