3 STUDY OBJECTIVES AND ENDPOINTS

STUDY OBJECTIVES	STUDY ENDPOINTS		
Primary			
To evaluate the efficacy of Phagenyx® treatment in reducing the severity of unsafe swallows.	Swallowing safety of a bolus based on PAS of each swallow, determined by a VFSS 48 hours after completion of investigational treatment, converted to a trichotomized ordinal response of safe (PAS 1-3), penetration (PAS 4-5), or aspiration (PAS 6-8). Each patient contributes up to 12 post-treatment repeated measurements (PAS) including 6 swallows of thin and 6 swallows of nectar.		
Secondary			
To evaluate the efficacy of Phagenyx treatment in improving nutritional management.	Functional Oral Intake Scale (FOIS) at 7 days following the last investigational treatment.		
	Dysphagia Severity Rating Scale (DSRS) at 7 days following the last investigational treatment		
Exploratory			

CONFIDENTIAL Page 30 of 71

STUDY OBJECTIVES	STUDY ENDPOINTS
To further characterize the efficacy of Phagenyx® treatment in reducing the severity of unsafe swallows.	The severity of unsafe swallows will be further evaluated via: O PAS outcome by each consistency (thin and nectar) O Physiologic measurement obtained using the Modified Barium Swallow Impairment Profile (MBSImP) metrics will be extracted from the thin and nectar swallows by the core lab by using the baseline and follow up VFSS data. These validated and reliable metrics of critical swallowing movements will be explored for their relationship to the primary study endpoint (PAS). O PAS dichotomized as safe (PAS 1-3) or
To evaluate the efficacy of Phagenyx® treatment on nutritional management changes.	unsafe (PAS 4-8) Nutritional management improvement will be evaluated via: Dysphagia Severity Rating Scale (DSRS) at 14 days or discharge, whichever is first, and at 11 weeks following the last investigational treatment. Time from baseline to removal of enteral feeding (i.e., removal of NG tube or PEG or transition to oral feeding, or first diet upgrade) Functional Oral Intake Scale (FOIS) at 7 days, 14 days or discharge, whichever is first, and 11 weeks following the last investigational treatment
To evaluate the efficacy of Phagenyx® treatment on improving quality of life.	Quality of life (QOL) will be assessed baseline and 11 weeks following the last investigational treatment via the following instruments: o EuroQoL-5 Dimension Questionnaire (EQ-5D) and EuroQoL-Visual Analogue Scale (EQ-VAS)

CONFIDENTIAL Page 31 of 71

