5 STUDY POPULATION

5.1 INCLUSION CRITERIA

CONFIDENTIAL Page 34 of 71

To be eligible to participate in this study, an individual must meet all of the following criteria:

- 1. Age \geq 18 and \leq 90 years.
- 2. Acute ischemic or hemorrhagic cerebral stroke within 7-28 days of baseline VFSS.
- 3. Score of 0 or 1 on NIHSS question 1a, Level of Consciousness.
- 4. *Moderate to severe dysphagia (PAS ≥4) on baseline VFSS (Baseline VFSS must meet the threshold criteria of demonstrating a PAS of ≥ 4, in three of the six boli (5 mL/1 tsp/bolus), during swallowing "thin liquid" barium media as assessed by the clinical staff administering the VFSS) unless its deemed too high risk then only 2 swallows will qualify.
- 5. Willing and able to have the Phagenyx® Catheter placed transnasally.
- 6. Willing and able to provide informed consent.
- 7. Stated willingness to comply with all study procedures and availability for the duration of the study.

*Note that the baseline VFSS will include testing with both thin liquids (up to 6 swallows) and nectar liquids (up to 6 swallows). For inclusion criterion 4, only the thin liquid swallows on the baseline VFSS will be considered. However, for descriptive statistics and other analyses, both the thin liquid and nectar liquid swallows on the VFSS will be considered.

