4. STATISTICAL METHODS

4.1. Statistical Hypotheses

The primary efficacy analysis is based on an ordinal logistic model of PAS (1-8 scale) of each bolus, determined by VFSS 48 hours following the last investigational treatment, and converted to a trichotomized response as follows: Safe (PAS 1-3), Penetration (PAS 4-5), or Aspiration (PAS 6-8). Hypothesis testing will be a superiority test performed on the main effect of treatment, β_{trt} , i.e., the difference in cumulative log odds between treatment groups, with $\beta_{trt} > 0$ indicating the PES group has higher odds of a safer responses than the control group.

- Primary Efficacy Endpoint: The null hypothesis is that $\beta_{trt} \leq 0$ (PES does not result in safer swallows than the control treatment), and the alternative hypothesis is that $\beta_{trt} > 0$ (PES results in safer swallows than the control treatment).
- If the primary endpoint meets statistical significance then formal testing and analysis for the secondary endpoint will be carried out.

The analysis of the secondary endpoint of FIOS is based on a Cochran-Mantel-Haenszel (CMH), stratified by site and baseline PAS, using the modified ridit score and test of "row mean scores different" to take into account the ordered nature of the response.

The analysis of the secondary endpoint of DSRS is based on an ANCOVA model of mean DSRS 48 hours after the last study treatment, adjusting for baseline. Hypothesis testing will be a superiority test performed on the main effect of treatment, δ , with $\delta \ge 0$ indicating the PES group has lower mean DSRS than the control group.

• Secondary Efficacy Endpoint of DSRS: The null hypothesis for the $\delta \leq 0$ (PES does not result in lower DSRS), and the alternative hypothesis is that $\delta > 0$ (PES results in lower DSRS).

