4.5. Statistical Tests and Decisions at the Interim and Final Analyses

4.5.1. Test Statistics

For the primary endpoint, independent increments of the normally distributed Wald statistic $Z = \hat{\beta}_{trt}/\widehat{SE}(\hat{\beta}_{trt})$, calculated using the GEE method with a robust sandwich estimator, are used for hypothesis testing and conditional power (CP) calculations. For the secondary endpoint, independent increments of the normally distributed Wald statistic $Z = \hat{\delta}/\widehat{SE}(\hat{\delta})$ is calculated based on estimates of treatment effect and standard error from the ANCOVA model. Conditional power is defined as the probability of reaching statistical significance at the planned final analysis (N=180) conditional on the observed effect size, assuming the current observed effect size is the true effect size.

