4.6.3 Exploratory Efficacy Analysis

Exploratory endpoints are as follows:

- The severity of unsafe swallows will be further evaluated via:
 - o PAS outcome by each consistency (thin and nectar)
 - o Physiologic measurement obtained using the Modified Barium Swallow Impairment Profile (MBSImP) metrics will be extracted from the thin and nectar swallows by the core lab by using the baseline and follow up VFSS data. These validated and reliable metrics of critical swallowing movements will be explored for their relationship to the primary study endpoint (PAS).
 - o PAS dichotomized as safe (PAS 1-3) or unsafe (PAS 4-8)
- Nutritional management changes will be evaluated via:

- Dysphagia Severity Rating Scale (DSRS) at 14 days or discharge, whichever is first, and at 11 weeks following the last investigational treatment.
- Time from baseline to removal of enteral feeding (i.e., removal of NG tube or PEG or transition to oral feeding, or first diet upgrade)
- Functional Oral Intake Scale (FOIS) at 7 days, 14 days or discharge, whichever is first, and 11 weeks following the last investigational treatment
- Quality of life (QOL) will be assessed baseline and 11 weeks following the last investigational treatment via the following instruments
 - EuroQoL-5 Dimension Questionnaire (EQ-5D) and EuroQoL-Visual Analogue Scale (EQ-VAS).
- General stroke health outcomes assessed by:
 - o Time to discharge from site in which treatment is received
 - o Discharge destination from the site in which treatment is received
 - o Patient location (home, institution) at 11 weeks
 - Days on antibiotics during hospital stay
 - NIH Stroke Scale (NIHSS) at baseline and 14 days or discharge, and 11-week follow up
 - o Modified Rankin Scale (mRS) at baseline, 14 days, and 11 week follow up
 - o Barthel Index (BI) at baseline, 14 days or discharge, and 11-week follow up
 - New onset pneumonia, using a standardized definition adapted from the STROKE-INF study²⁶ at baseline, 48 hrs, 7 days, and 14 days or discharge
 - Hospital readmission rate
 - o Number of CXR (related to suspect pneumonia)

Exploratory endpoints will be summarized by treatment group, and may be analyzed using appropriate statistical models with adjustments for key prognostic covariates. No multiplicity adjustments will be made for exploratory analyses.

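### The primary test of β_trt is a test of thin-liquid swallows only, although the primary endpoint covers both thin and nectar swallows

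*SAP*

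**What the plan says.** SAP 4.6.1 (printed under 4.8) fits a cumulative logit model to the trichotomized PAS of each bolus. The model "will include treatment, bolus consistency, baseline maximum PAS, and treatment by consistency interaction as predictors". The equation contains a treatment term, a nectar term and their product, "and a consistency indicator $nectar_i$ (1=nectar, 0=thin").

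SAP 4.1 sets the null hypothesis β_trt ≤ 0 and describes the comparison as "a superiority test performed on the main effect of treatment", without naming a consistency. SAP 4.5.1 builds both the test and the conditional power on that coefficient divided by its sandwich standard error: "For the primary endpoint, independent increments of the normally distributed Wald statistic". SAP 4.5.2 applies this at 60 patients: "At this analysis, conditional power (CP) will be calculated for the primary endpoint", with a non-binding futility recommendation below 5%.

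The endpoint is wider. Protocol section 3 states: "Each patient contributes up to 12 post-treatment repeated measurements (PAS) including 6 swallows of thin and 6 swallows of nectar". SAP 4.6.3 lists "PAS outcome by each consistency (thin and nectar") among the exploratory endpoints. Only eligibility rests on thin liquid alone, and the note to inclusion criterion 4 in Protocol 5.1 adds: "However, for descriptive statistics and other analyses, both the thin liquid and nectar liquid swallows on the VFSS will be considered". SAP 4.2 assumes one odds ratio, 2.23, not split by consistency.

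**The concern.** When a model contains a product term and the other factor is coded 0/1, the coefficient of treatment is its effect at the level coded 0. Here that level is thin liquid, so the coefficient named in the hypothesis is not an effect over both liquids.

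Two things follow. First, the words and the formula in the SAP disagree: a programmer who follows the main-effect description and one who follows the printed equation would compute different primary Z values. Second, the treatment effect on nectar does not enter the primary Z, the conditional power at either look or, if it is taken from β_trt, the reported odds ratio. The gate to the secondary endpoints and the efficacy stop at 120 patients depend on the same Z. Someone who has read only the endpoint definition would not know that half of the swallows contribute only indirectly, through the cut-points, the baseline slope and the covariance.

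**Working it through.** **Algebra on the printed model.** Write β_int for the treatment-by-nectar coefficient. PES minus control on the cumulative log odds is:

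- thin (nectar = 0): β_trt
- nectar (nectar = 1): β_trt + β_int
- equal weight over 6 + 6 swallows: ½β_trt + ½(β_trt + β_int) = β_trt + 0.5·β_int

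The last line equals β_trt only if β_int = 0.

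**The plan's own figures.** The Lan-DeMets O'Brien-Fleming boundaries at information 2/3 reproduce as 2.5093 and 1.9929 (SAP 4.5.3), and 180/0.8 = 225 and 270/0.8 = 337.5, rounded up to 338. The 95% power (SAP 4.2) cannot be reproduced: the documents give no control-arm probabilities, within-patient correlation or odds ratio by consistency. It implies a mean Z of 1.9929 + 1.6449 = 3.638, hence a standard error of ln(2.23)/3.638 = 0.802/3.638 = 0.220 for whichever contrast was simulated.

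**Analytic size.** Suppose the averaged contrast has 95% power at a common odds ratio of 2.23. With benefit on nectar only, its mean is halved and its power is Φ(3.638/2 − 1.9929) = Φ(−0.174) = 43%. If instead β_trt has the 95% power, and its standard error is 1.01 to 1.18 times that of the averaged contrast (the simulated range), the averaged contrast has Φ(3.638 × 1.01/2 − 1.9929) = 44% to Φ(3.638 × 1.18/2 − 1.9929) = 56%. In either case β_trt targets zero.

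**Simulated size.** Two simulations were run under different assumptions. Both used 180 patients, 12 swallows, working independence (the SAP names no working correlation), patient-clustered sandwich errors and a single test at 1.9929, with no interim looks or sample size change.

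- Simulation A: control thin 35% safe, 25% penetration, 40% aspiration; nectar 50% safe; baseline slope −0.25 per PAS point; seven pairs of latent correlations, from 0.55 within and 0.25 between consistencies to 0.9 and 0.7; 2000 trials each.
- Simulation B: control thin 35/20/45%, nectar 55/20/25%; no baseline term; 1:1 allocation; 1500-2000 trials. Correlations ran over 0.4-0.7 within and 0.2-0.5 between for the common-effect row, and were 0.5 and 0.3 for the other rows.

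Rejection rates, β_trt versus β_trt + 0.5·β_int:

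| True odds ratio (thin / nectar) | A | B |
|---|---|---|
| 1 / 1 | 2.2-2.6% vs 1.8-2.5% | 2.2% vs 1.8% |
| 2.23 / 2.23 | 87-98% vs 91-99.6% | 94.0-98.8% vs 96.1-100% |
| 1 / 2.23 | 2-3% vs 38-63% | 2.2% vs 62.8% |
| 2.23 / 1 | 87-98% vs 39-65% | 98.4% vs 65.2% |
| 2.23 / (1/2.23), stress case | 87-98% vs 1.9-2.5% | 98.3% vs 2.7% |
| 1.5 / 3.3 (average √(1.5 × 3.315) = 2.23) | not run | 54.1% vs 99.6% |

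In B with a nectar-only benefit, the mean estimate of β_trt was −0.003 and of the averaged contrast 0.401, which is half of 0.802 as the algebra requires.

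**First futility look.** Under the current trend at information t = 60/180 = 1/3, CP = Φ[(Z/√t − 1.9929)/√(1 − t)]. CP < 5% means Z < √(1/3) × (1.9929 − 1.6449 × √(2/3)) = 0.577 × 0.650 = 0.375. If the thin effect is zero, that happens with probability Φ(0.375) = 65%, whatever the effect on nectar. Simulating 60 patients (1000 trials, nectar odds ratio 2.23) gave 65% with β_trt at all three correlation settings, against 16%, 22% and 28% with the averaged contrast.

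**The case against.** The strongest reply is that this is an internal contradiction rather than a settled thin-only test. SAP 4.1 describes an overall treatment difference in words, and the analysis code and Simulation Report are not in the documents, so the right contrast may already be in use. That is fair about what will be run. It does not rescue what is written, because the symbol, the coding and the Z formula together give the thin effect.

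Second, the large gaps need effects that differ by liquid, and SAP 4.2 plans a single odds ratio. This stands: with a common effect the loss is one of precision only. But the SAP includes the interaction and so allows for unequal effects.

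Third, simulations A and B omit the VFSS stopping rule and the worst-value imputation. Where nectar is skipped after a thin stop, nectar values are filled in because of thin results. With both rules added, and nectar assumed skipped in 25%, 50% or 100% of thin stops, nectar-only rejection by the averaged contrast falls to 26-47%, 17-36% or 9-20%, while β_trt stays at 1.5-3%. In the thin-only case the averaged contrast rises to 53-86% at 100% skipping. The skip rate is not in the documents. This reduces the size of the gap and leaves its direction.

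Fourth, the futility recommendation is non-binding, and the 65% uses 1.9929 as the final boundary. SAP 4.5.4 prints 2.5093 instead; with that value the cutoff is 0.577 × (2.5093 − 1.3431) = 0.673 and the rate is 75%.

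**Conclusion.** The concern holds. As printed, the primary hypothesis, the Wald statistic and the conditional power concern thin liquid only, while the endpoint covers both liquids and by-consistency results are exploratory. This follows from the equation and the coding and needs no assumption.

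Its practical size depends on how far the two effects differ. At a common odds ratio of 2.23 the cost is small. With benefit confined to one liquid, the two contrasts can lead to opposite conclusions. The rates rest on assumed category probabilities and correlations, a fixed-sample test and, for the main figures, no VFSS stopping.

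Three limits apply. The test is valid for the thin-liquid null. The stated 95% power is not shown to be wrong. Neither contrast has the higher power in every scenario, so the choice should follow the intended estimand. It still needs settling before any unblinded look, because it fixes what the confirmatory test means and cannot credibly be chosen after data are seen.

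**What to change.** Before the first interim, define the primary contrast as β_trt + 0.5·β_int with its sandwich standard error. Coding consistency −0.5 for thin and +0.5 for nectar makes β_trt that contrast directly. Use it in the hypothesis (SAP 4.1), the Wald statistic, conditional power and final combination test (4.5.1 to 4.5.4) and the reported odds ratio (4.6.1). Keep the separate thin and nectar effects in the exploratory analysis already listed.

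Dropping the interaction is another route, but it does not give equal weight when effects differ: in simulation B with a nectar-only benefit, that model estimated 0.362 where the equal-weight contrast estimated 0.401. If thin liquid is the intended question, say so in the hypothesis and in the endpoint definition of both documents.

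The cost is wording in SAP 4.1, 4.5 and 4.6.1 and one line of code (plus the protocol's endpoint text if thin only is chosen). The Simulation Report must be checked for the contrast it used, and its power and conditional-power zones re-run if that differs. Sample size, alpha, boundaries and data collection do not change.
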